The rationale for the duration of the interventions, follow up, and blinding procedures: The proposed study is of standard duration for the geriatric population requiring 12 weeks or longer trials to document antidepressant efficacy.

4.0 *Research Design and Methods: Describe in detail the design and methodology of the study.

Subjects: We anticipate screening about 100 subjects to recruit 60 older depressed adults (>60 y.o.) who will be randomized to receive 20-120 mg of levomilnacipran blindly with increment dose titration 20 mg per day -3 days; 40 mg per day-3 days. Based on efficacy and tolerability, we will increase by 40 mg per day each following week 2nd-4th week the maximum recommended doses is 120 mg per day. The comparison group will receive similar blinded titration with matching placebo. Doses of the drugs will be adjusted according to individual tolerability and safety. We expect an attrition rate of about 10% based on our prior experience thus 54 subjects will complete the study. Patients will be assessed pre-treatment; and then weekly during the first four weeks and bi-weekly thereafter. At all visits, clinical ratings of mood, vital signs, and safety will be obtained. Inclusion criteria: 1) The presence of a major depressive disorder diagnosed according to the DSM-IV criteria. 2) A 24-item Hamilton Rating Scale for Depression (HAMD) score of 17 or higher at baseline. 3) Mini-Mental State Exam (MMSE) score > 24.

Exclusion criteria: subjects will be excluded if they had 1) any current and/or lifetime history of other psychiatric disorders (except unipolar depression with or without comorbid generalized anxiety disorder), or 2) recent unstable medical or neurological disorders; 3) any disabilities preventing their participation in the study or in the MRI; 4) diagnosis of dementia; 5) acute suicidality; 6) those with known allergic reactions to milnacipran, uncontrolled narrow angle glaucoma, seizures, poorly-controlled hypertension or ischemic changes on ECG, serotonin syndrome, or the recently used MAOIs within last 4 weeks; 7) ineligible for MRI (e.g., metal in the body or claustrophobia)

Primary outcome will be measured and defined as follows: 1) Remission will be defined as HAMD scores of 6 or less for three consecutive weeks and at week 12; 2) Improvement in depression severity using HAMD scores.

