Randomization and treatment schedule: After all screening and baseline test results are reviewed and eligibility criteria are confirmed, medications will be dispensed if patients continue to meet eligibility criteria and sign the informed consent form. All eligible subjects will be randomized to levomilnacipran or placebo group using a computer-generated random assignment scheme, which assigned subjects in a 1:1 ratio to each group. Randomization will be done prior to subject s being assigned to the groups.

Follow up assessment: The follow up will take place weekly for the first four weeks of treatment, every two weeks for the remainder of the study. Each follow up assessment will include measures of efficacy and safety. The weekly frequency of contact with all subjects will serve as an additional safeguard to monitor worsening of depression, as well as the emergence of side-effects or suicidal ideations.

Study medications and treatment procedures. Subjects will be randomized to: 1) LMIL20-120 mg per day or 2) matching placebo. The allowed range of the drugs according to tolerability and efficacy assessments will be between 20-120 mg per day for LMILN. The dose finding procedures will be only performed in the first four weeks and after that will remain stable until the end of the acute trial, as it worked in our pilot study. We will assess the optimal dose of LMIL based on tolerability and safety in this population. The balance will be maintained between the efficacy and tolerability of medications. If symptoms worsen, the study drug will be tapered and discontinued. Subjects will be referred for clinical care at UCLA or the community. The PI will continue the observation for safety until the appointment is scheduled with the primary psychiatrist. The dose will be titrated according to the titration schedule, including if side-effects are mild or well tolerated and if CGI scores for improvement is 3 or higher. The titration rate is based on the currently recommended titration to achieve the greatest efficacy that may not work for geriatric patients. For that reason, we have safeguards against rapid titration with potential side-effects that will require a slower titration or staying at a lower dose.

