experimental tests. Please describe the tests, provide a rationale for providing participants with the experimental test results and explain what, how and by whom participants and their health care provider will be told about the meaning, reliability, and applicability of the test results for health care decisions.

0

o 4.1.2

 Will tests be performed by a Clinical Laboratory Improvement Amendments (CLIA) approved lab?

o Yes No

5.0 *Indicate how much time will be required of the subjects, per visit or contact, and in total for the study.

This study will require that the participants make up to 10 visits in 12 weeks (three months) to the study site during their participation. Each participant will be required to commit approximately 10 hours in 3 months: visit 1 (2 hours); visit 2 (2 hours); visit 3-9 (each 30 minutes); visit 10 (2 hours).

6.0 *Statistics and Data Analysis: Describe the proposed statistical procedures or descriptive analyses for the study. If applicable, indicate how the sample size was determined.

DATA ANALYSIS. Data will be analyzed using the SAS (v9.3) statistical package. Data will be examined initially to identify issues such as departures from normality, which might suggest the need for transformation (e.g., logarithmic). Demographic variables (e.g., age, gender, etc.) and variables characterizing the course of depression (e.g., age of onset, chronicity, number of episodes, length of the current episode, etc.) will be compared by treatment group and examined in relation to outcome variables; this would define one possible set of appropriate covariates, if needed. Correlations (a) among outcome measures and (b) among potential covariates in the same domain will be examined to eliminate redundancy via possible data reduction, e.g., formation of composite scores or selection of single measures from sets of highly inter-correlated variables. Corrections for multiple significance testing will be performed within measurement domains when multiple measures are involved using Simes methods. Tests of the primary hypotheses that specify a predefined outcome measure will not be adjusted.

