Hypothesis 1: The primary analyses will focus upon HAM-D24 scores and will be analyzed using general linear mixed model analysis (e.g., SAS PROC MIXED). The two treatment groups will be compared for time course of HAM-D-24 with the initial endpoint EOT at 12 weeks. Covariates may be included in the model as noted above. In addition, likelihood ratio ?2 comparison will examine group differences in remission (HAM-D24 =6) and response (HAM-D24 =10) at EOT. Analyses for the cognitive outcome variables will be akin to those described above for the continuous HAM-D scores. As noted in the Neuropsychological Assessment section, there are four cognitive domains that are being assessed. Of these, the two primary cognitive domains of interest for this proposal are Cognitive Control and Episodic Memory. A separate general linear mixed model as above will be estimated using these two domain scores as dependent variables. The remaining domains, namely Verbal Fluency and Information Processing/Attention will be examined as secondary outcome measures. Apathy will be examined using the AES total score and quality of life using SF-36 scores in similar mixed models.

Hypothesis 2: We will examine adverse events in the two treatment groups. A detailed comparison of the number as well as type of side-effects in the two treatment groups will be conducted using chi-square tests.

Hypothesis 3: LMIL will lead to improved functional connectivity in brain network activity as measured with resting state (rs-) fMRI, and plasticity in brain macro- and micro-structure as measured with structural MRI and DTI compared to the PBO. To address these hypothesis, summary MRI measures (e.g., substructure volume, diffusion metrics) will be included in the GLMMs as "covariates of interest." For whole brain or structure voxel-level or point based measures (e.g., thickness or activation), the GLMMs will be implemented in R (www. R.org). Time (of scan) will be treated as a continuous variable with random intercepts and slopes to account for within-subject correlations between repeated measurements to assess change and interactions amongst the interventions. Difference scores between baseline and 12-week follow-up may be substituted for some analyses. FDR and/or permutation methods will be used to control for multiple anatomic comparisons in whole-brain contexts.

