Hypothesis 4: The role of brain neuroimaging biomarkers in variability of treatment response is examined in this Hypothesis. Predictor variables: We predict that baseline measures of neuroimaging biomarkers of emotional responsivity; working memory and connectivity will be related to treatment outcomes. These predictions will be evaluated in the context of the models described above (i.e., general linear mixed model) by adding the posited prognostic variable as an additional predictor.

Power. With a significance level (alpha) of 0.05, 80% power, and N = 30 in each treatment arm, we can detect an effect size (ES, difference between group means as a multiple of the standard deviation) of 0.7. Using appropriate covariates such as age of onset, chronicity, and number of episodes can be expected to reduce variance and increase power for a given difference in mean, hence the two-sample power computations are conservative for this situation. This study will thus yield sufficient pilot data to justify conducting a larger study in the future.

Data management. Data management and analysis support will be provided by the UCLA SI-STAT services and [name] will supervise the data gathering duties of the study coordinator, including reviewing all data entry forms. 1. Randomization. The prestudy forms must be submitted before a patient can be randomized. A separate portion of the database will also be maintained for patients screened but not enrolled or randomized. Randomization schedules will be prepared in a masked manner by the statistician. 2. Data submission and quality control. Data forms will be delivered from the originating location to the central data unit within one week of being generated. When errors, omissions, or unclear information is detected on the paper forms, a copy

will be returned for corrections. The data manager will generate monthly reports summarizing missing and incorrect data will be sent to the PI. 3. Data confidentiality. Patient study forms will be stored in locked file cabinets and will be accessible only to authorized personnel. A shredder will be used to discard all unwanted study documents. Access to the data will be password protected with only authorized persons having knowledge of the password.

ID: IRB#14-001827

View: NEW 11.1 - Characteristics of the Study Population

Warning: Save your work at least every 15 minutes by clicking \$Save\$ or \$Continue.

Characteristics of the Study Population

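### Two primary mood outcomes, a rule leaving primary tests unadjusted, and no statement of which decides: about 8–9% false-positive risk if either may count

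*Combined protocol and SAP*

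**What the plan says.** - **Primary outcomes (10.1 item 4.0).** The definition opens "Primary outcome will be measured and defined as follows: 1) Remission will be defined as HAMD scores of 6 or less" and goes on to list improvement in HAMD severity as a second item.
- **Multiplicity (10.1 item 6.0, Data Analysis).** One sentence plans Simes corrections within a measurement domain that has several measures. The next says "Tests of the primary hypotheses that specify a predefined outcome measure will not be adjusted".
- **Hypothesis 1 analysis (10.1 item 6.0).** The primary analyses centre on HAM-D24 in a mixed model: "The two treatment groups will be compared for time course of HAM-D-24 with the initial endpoint EOT at 12 weeks". Likelihood-ratio comparisons of remission and response at end of treatment are added. Of four cognitive domains, "the two primary cognitive domains of interest for this proposal are Cognitive Control and Episodic Memory".
- **Aims (10.1 item 2.0).** Hypothesis 1 calls mood primary, and cognition, apathy and quality of life secondary.
- **Power (10.1 item 6.0).** "With a significance level (alpha) of 0.05, 80% power, and N = 30 in each treatment arm, we can detect an effect size", defined as the "difference between group means as a multiple of the standard deviation) of 0.7".

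No section gives an order of testing, an alpha split or a rule for success.

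**The concern.** Two outcomes carry the word primary, and the rule on adjustment can leave each at 0.05. A reader cannot tell from the plan whether success needs one of them, both, or a particular one. If one is enough, the error rate for the main efficacy question exceeds the 0.05 used to size the trial. The choice between a significant remission result and a null HAM-D24 result (or the reverse) would then be made after the data are seen.

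The leading test is also not pinned down. A group-by-time test over all visits and a single week-12 contrast are different tests of the same scores, and they can disagree.

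**Working it through.** **1. The plan's own figure.** Inputs: alpha 0.05, 80% power, 30 per arm, 1:1 allocation (10.1 items 4.0 and 6.0). Two-sided testing is assumed, because sidedness is not stated.

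Detectable effect = (z₀.₉₇₅ + z₀.₈₀) × √(2/n) = (1.960 + 0.842) × √(2/30) = 2.802 × 0.258 = **0.72**. An exact t calculation gives 0.74. Both round to the printed 0.7, so there is no separate error here. At exactly 0.7, power is 77.4% (t: 76.0%). The calculation spends the whole 0.05 on one comparison of means.

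**2. Two tests at 0.05, either sufficient, independent.** 1 − (1 − 0.05)² = 1 − 0.9025 = **9.75%**.

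**3. Allowing for correlation.** Remission is cut from the same scale as severity, so the tests overlap. With bivariate normal test statistics under the null, P(either |z| > 1.96) is **9.1%** at correlation 0.5 and **7.8%** at 0.8. The document gives no correlation. As a guide, a normal score and its own cut at proportion p correlate at φ(z_p)/√(p(1−p)). At p = 0.35 this is 0.370/0.477 = 0.78. A remission rule spanning several weeks, as in item 4.0, would probably correlate less with the week-12 score.

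**4. Direct simulation.** 40,000 null trials per scenario, 30 per arm: a t-test on the score (standing in for the mixed model) and a likelihood-ratio chi-square on remission cut from that score at a single visit. Remission was set at 30–40%, the range item 4.0 gives without naming the endpoint. Either test significant: **8.0–8.9%**. The likelihood-ratio test alone ran at about 5.0–5.9%, so a little of the excess is its small-sample behaviour.

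**5. Wider families, for comparison only.** Assumptions: response 45–55%; correlation 0.2 or 0.5 among the HAM-D and cognitive scores.

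| Tests counted, any one sufficient | Simulated | If independent |
|---|---|---|
| HAM-D24, remission | 8.0–8.9% | 9.75% |
| plus response | 10.2–11.0% | 14.3% |
| HAM-D24, remission, two cognitive domains | 15.2–17.5% | 18.5% |
| all five | 17.2–19.4% | 22.6% |

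**6. What each remedy costs.**

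| Rule | Error | Power at 0.7 | Detectable at 80% |
|---|---|---|---|
| HAM-D24 at week 12 as sole primary | 5% | 77.4% | 0.72 |
| Equal split, 0.025 each | at most 5% | 68.1% | 0.80 |
| Hochberg step-up on both | 4.4–4.7% (simulated) | not computed | not computed |

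Under the equal split, n per arm for 0.7 rises from 33 to 39.

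**7. Time course or week 12.** The visit schedule gives eight post-baseline visits (weeks 1–4, 6, 8, 10, 12), so a full group-by-time test has 8 degrees of freedom. Where a week-12 contrast has 80% power, that test had 23% power for a linear effect with autoregressive correlation 0.8 per week, and 98% for an effect that plateaus at week 4 with compound symmetry 0.7. These covariances are assumed. The range shows that the choice can decide the result; it does not show in which direction.

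**The case against.** Leaving several primary tests unadjusted is not wrong in itself. If both outcomes had to succeed, or if they were tested in a fixed order, no adjustment would be needed. The plan does not say that either one suffices, so the 8–9% is conditional. This stands, and it is why the conclusion is worded with an if.

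Item 6.0 can also be read as already making HAM-D24 the sole primary, since its primary analyses centre on that score and the power statement covers one comparison of means. Alternatively, the Simes sentence can be read as covering all mood measures. Either reading removes the inflation, but the first conflicts with the two-item list in item 4.0 and the second with the exemption sentence that follows. Some text has to change under every reading.

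A reader might infer that every Hypothesis 1 test is exempt, giving 17–19% error, or that a memory result could be presented as the primary finding. The documents do not support this. Item 2.0 makes cognition secondary, the word primary applied to two cognitive domains reads naturally as a ranking among the four, and response is never listed as a primary outcome.

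Finally, this is a pilot meant to estimate effect sizes, which lowers the stakes. It does not remove them: the lay summary anticipates superiority on both symptoms and remission, and the results are meant to justify a larger study.

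**Conclusion.** The concern holds in a limited form. Two outcomes are named primary, the exemption can leave both at 0.05, its neighbouring sentence points the other way, and nothing says which outcome decides. If either may count, the false-positive chance is about 8–9%, with 9.75% as the independent-tests figure. This rests on two-sided tests and on assumed correlations or remission rates.

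Two stronger statements should be avoided. The plan does not claim a familywise rate of 5% and then break it: 0.05 appears only as a per-test level for one comparison. Nor does it say that any single significant test makes the trial positive; that possibility comes from its silence. The undefined HAM-D24 contrast is a real second gap, but its effect on power cannot be sized from the documents. The text should be corrected before unblinding.

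**What to change.** Reconcile section 10.1 items 4.0 and 6.0 as follows:

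1. State that the single primary test is the levomilnacipran–placebo difference in HAM-D24 at week 12, a one-degree-of-freedom contrast from the mixed model, two-sided at 0.05, and that only this test is unadjusted.
2. Move remission and response to secondary, under the planned Simes-type correction within the mood domain (Hochberg's step-up is the natural form for individual claims). List the members of that family. With remission and response alone, a lone significant result would need p ≤ 0.025.
3. Label Cognitive Control and Episodic Memory as key secondary, in line with item 2.0, keeping the plan's within-domain correction.
4. Report the HAM-D24 time-course test as supportive.

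This choice fits the HAM-D24 emphasis and the power statement already in item 6.0. It leaves the primary test's power unchanged, whereas an equal alpha split would lower it from 77.4% to 68.1% at an effect of 0.7. The cost is a few sentences and no new data. The downside is that remission gives up primary status and faces a corrected threshold. Pooling all secondary outcomes into one family is not needed; it would replace the plan's within-domain structure and is a matter of preference.

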 1.1 If you indicated that personal identifiers will be maintained for future research, provide the following information: a) How the information will be securely handled and stored b) assure confidentiality, and c) who will have access to the identifiers and/or codes

2.0 Describe any additional steps, if any, to be taken to assure that the subjects' identities and any personal identifying information are kept confidential.

ID: IRB#14-001827

View: NEW 10.1 - Study Summary - Research Study

Warning: Save your work at least every 15 minutes by clicking &Save or &Continue.

Study Summary - Research Study -

1.0 Study Materials: As applicable to this study, attach the following:

- Protocol, Dissertation Proposal or Study Plan
- Preliminary Data
- Surveys, Questionnaires or other instruments to be used with study participants
- References

Document Name	Document Version #
LMIL Tables and Figures.docx	0.01
LMIL Bibliography and References cited.docx	0.01
Levomilnacipran proposal 042014.docx	0.01

2.0 *Specific Aims: Indicate the purpose of the research, specifying the problems and/or hypotheses to be addressed.

Specific Aims and Hypotheses:

Primary Aim: To compare the efficacy and generate estimates of the effect sizes on primary and secondary outcomes between the treatment groups in a 12 week double-blind placebo controlled treatment trial with levomilnacipran compared to placebo. Hypothesis 1: We will observe detectable differences in primary (mood) and secondary outcomes (cognition, apathy and quality of life) between the two treatment groups favoring LMIL.

Aim 2: To test whether the two treatment conditions will show no difference in tolerability and safety. We will particularly focus on cardiovascular status (blood pressure, heart rate, ECG changes)

Hypothesis 2: There will not be a difference in the rate of adverse events between the two groups.

Exploratory Aim 3: To compare the patterns of functional and structural connectivity in the two intervention groups. Hypothesis 3: LMIL will lead to improved functional connectivity in brain network activity as measured with resting state (rs-) fMRI, and plasticity in brain macro- and micro-structure as measured with structural MRI and DTI compared to the PBO.

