Levomilnacipran use in geriatric depression: Levomilnacipran is a novel serotonin and norepinephrine reuptake inhibitor (SNRI) for the treatment of major depressive disorder. The drug differs from previously available SNRIs in having twice the potency for norepinephrine versus serotonin reuptake inhibition. In four of the six short-term clinical trials, levomilnacipran was statistically significantly more efficacious than placebo. The only available relapse prevention study did not show reduction in time to relapse, perhaps because relapse rates were low. The commonest adverse events occurring twice as often as on placebo were nausea, hyperhidrosis, constipation, tachycardia, vomiting, erectile dysfunction, palpitations, and ejaculation disorder. In a few patients, hypertension or orthostatic hypotension may occur, which is of importance in older adults- we will follow these parameters in the study. Levomilnacipran, given its action profile with dual action on serotonin and norepinephrine reuptake inhibition, may also be helpful for such prominent features of geriatric depression, as apathy, and therefore, improve the overall quality of life.

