Neuropsychological assessment (at baseline, at 12 weeks): Our approach to cognitive assessment and analyses is based on our prior work and benefits from input from [name]. We will use a focused test battery developed by [name], assessing domains which have shown impairment in geriatric depression, according to prior research by our group45 and others: 9,46-48 (1) cognitive control, which relates to mental flexibility and inhibition and adjustment of behavior; (2) verbal fluency, which requires strategic searching/organization of verbal knowledge; (3) episodic memory: including explicit memory for verbal and nonverbal information; and (4) information processing speed and attention, including an indices of complex and sustained attention. Most of the measures have 2 or 4 alternate forms that will be important in repeating them during follow up. In addition to the cognitive outcome measures, we will include a brief word reading test, the WAIS-IV Test of Premorbid Functioning (TOPF), a revision of the Wechsler Test of Adult Reading (WTAR),49 to estimate an individual premorbid cognitive functioning. We will conduct a confirmatory factor analysis to assess the goodness of fit of our a priori domain assignments. Finally, we will assess the validity of assignment to composite domains using confirmatory factor analysis. The tests variables derived from each and a priori composite domain assignment: Verbal Fluency (Category and Letter Fluency tests): Cognitive Control (Trailmaking test part B and Stroop Color-Word Interference test); Attention and Processing Speed (Trailmaking test part A; Stroop rapid color and word reading scores (averaged); Digit vigilance d-prime); and Episodic Memory (Rey Auditory Verbal Learning; Brief Visual Spatial Memory tests).

Safety evaluations. Physical examination and vital signs at baseline: pulse rate, systolic blood pressure, and body weight will be obtained at each visit, in addition to a 12-lead ECG at baseline, if any cardiac complaints are present. Laboratory tests (as listed below) will be performed at baseline. The UKU Side Effect Rating Scale,50 a comprehensive rating scale for monitoring adverse events of psychotropic drugs used in clinical trials, will be completed at all visits except screening.

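### A non-significant chi-square with 30 per arm cannot support the no-difference adverse-event hypothesis, and the Simes rule, which has no safety exemption, appears to lower detection further

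*Combined protocol and SAP*

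**What the plan says.** All references are to section 10.1 of the combined protocol and SAP.

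- **Specific Aims (item 2.0).** Aim 2 is "To test whether the two treatment conditions will show no difference in tolerability and safety", and its hypothesis is "There will not be a difference in the rate of adverse events between the two groups". No margin is given.
- **Statistics and Data Analysis (item 6.0), Hypothesis 2.** "A detailed comparison of the number as well as type of side-effects in the two treatment groups will be conducted using chi-square tests". The paragraph does not list the types, count them, or say whether the tests are adjusted.
- **Statistics and Data Analysis, opening paragraph.** "Corrections for multiple significance testing will be performed within measurement domains when multiple measures are involved using Simes methods". The one exemption follows: "Tests of the primary hypotheses that specify a predefined outcome measure will not be adjusted". Safety is neither named nor exempted.
- **Safety evaluations (item 4.0).** Side-effects are recorded on the UKU scale, described as "a comprehensive rating scale for monitoring adverse events of psychotropic drugs used in clinical trials". The number of items is not given.
- **Background and Significance (item 3.0).** "The commonest adverse events occurring twice as often as on placebo were nausea, hyperhidrosis, constipation, tachycardia, vomiting", followed by three more events, eight in all. Absolute rates are not given.

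**The concern.** The result hoped for under Hypothesis 2 is a failure to reject. A comparison with little power delivers that result easily, whether or not the drug has the excess of side-effects that the background describes. A multiplicity correction guards against declaring a difference falsely. Here the more important error is to miss a real one, so a correction works in favour of the stated hypothesis, and a longer list of side-effect types generally makes it stricter. What is at stake is a report that tolerability did not differ in older patients, resting on tests that could hardly have shown otherwise.

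**Working it through.** **Inputs from the plan.** 30 per arm, alpha 0.05 (taken as two-sided), 1:1 allocation, about 10% attrition (54 completers, 27 per arm), rate ratio of 2 for eight named events.

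**Assumptions.** Placebo rates of 5–30%; 8 side-effect types, matching the eight named events, with other family sizes for comparison; independent types; Pearson chi-square without continuity correction.

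**Step 1: the plan's own power figure.** It concerns a difference in means: (1.96 + 0.842) × √(2/30) = 0.72, which rounds to the stated 0.7. At exactly 0.7 the power is 77.4%. The gap is rounding and does not affect this point. No power figure is given for Hypothesis 2.

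**Step 2: chance of flagging one doubled side-effect, unadjusted.** Power = Φ[(d − z·SE0)/SE1], where d = p2 − p1, SE0 = √(2p̄(1 − p̄)/n), SE1 = √((p1(1 − p1) + p2(1 − p2))/n) and z = 1.96. For 10% vs 20%: SE0 = √(2 × 0.15 × 0.85/30) = 0.0922; SE1 = √(0.25/30) = 0.0913; (0.10 − 1.96 × 0.0922)/0.0913 = −0.88; Φ = 0.19.

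**Step 3: the same under a Simes-based correction over 8 types.** The strictest step uses alpha/8. The two usual step-up procedures, Hochberg and Benjamini-Hochberg (BH), were simulated with at least 40,000 trials per setting.

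| Placebo vs drug | Unadjusted | At alpha/8 | One of 8 doubled, Hochberg or BH | All 8 doubled, Hochberg / BH |
|---|---|---|---|---|
| 5% vs 10% | 11% | 2% | not run | not run |
| 10% vs 20% | 19% | 5% | 4% | 4% / 6% |
| 15% vs 30% | 28% | 9% | 8–9% | 9% / 13% |
| 20% vs 40% | 39% | 14% | 15–16% | 16% / 25% |
| 25% vs 50% | 52% | 22% | 24% | 27% / 41% |
| 30% vs 60% | 65% | 34% | 35–36% | 44% / 59% |

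With 27 per arm, the unadjusted figures for placebo rates of 10%, 15% and 20% are 17%, 26% and 36%.

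**Step 4: sensitivity to family size.** With 3 types, one doubled at 20% vs 40%, detection falls only from 39% to about 24%. With 20 types and one doubled, the relative loss is 77–92% for placebo rates of 10–20%.

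**Step 5: male-only events.** Two of the eight events can occur only in men. If half the patients are men (assumed, 15 per arm), 20% vs 40% gives SE0 = √(2 × 0.3 × 0.7/15) = 0.167 and SE1 = √(0.40/15) = 0.163. Then (0.20 − 1.96 × 0.167)/0.163 = −0.78, and power is about 22% instead of 39%.

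**Step 6: what an interval would show.** Suppose 3 of 30 are affected in each arm. The risk difference is 0, and its 95% half-width is 1.96 × √(2 × 0.1 × 0.9/30) = 0.15. The interval runs from −15 to +15 percentage points, which includes a doubling of a 10% rate (+10 points). The p-value alone hides this.

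**Step 7: cost of dropping the correction.** With 8 independent null types, the chance of at least one false flag is up to 1 − 0.95⁸ = 0.34.

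**The case against.** **The rule may not be meant for harms.** A reader might infer that the plan expressly applies Simes to side-effects. It does not. The sentence is general, follows text on reducing correlated outcome measures, and leaves measurement domain undefined for safety. The exemption is also arguable: it speaks of primary hypotheses in the plural, and only Aims 3 and 4 are labelled exploratory. This stands as a limit. Coverage is the natural reading, because only the efficacy aim is called primary and side-effect type is not one predefined measure, but it remains a reading.

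**The loss has no fixed size.** A reader might infer that the correction cuts detection by more than half. That holds in many settings but not all. With BH and all eight types doubled at 20% vs 40%, detection falls from 39% to 25%, a loss of a little over a third. Small families and high placebo rates also lose less.

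**One type does not settle Hypothesis 2.** The hypothesis concerns the overall rate, and the plan compares the number of side-effects as well as their type. If all eight events double independently, at least one is flagged with probability 82%, 93% or 98% unadjusted (for example 1 − 0.81⁸ ≈ 0.82), and 31%, 54% or 76% under a Simes-based procedure, for placebo rates of 10%, 15% and 20%. This is fair: the per-type figures show what can be said about a given side-effect, not about the whole profile. The correction still moves the result towards no difference.

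**The trial is a pilot, and individual safety decisions rest elsewhere.** Section 15.2 bases discontinuation on individual criteria and provides a monitoring committee. Nothing in the documents ties patient protection to these p-values. That limits the consequence to what is reported about tolerability.

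**Conclusion.** The point holds in a limited form. The main weakness is that Hypothesis 2 is the null, has no margin, and would be judged by tests that flag a doubled side-effect only 19–39% of the time at placebo rates of 10–20%. Non-significance then says little. The Simes rule, on its natural reading, makes this worse: about 4–6%, 8–13% and 14–25% with 8 types. These figures rest on assumed placebo rates, family size, procedure and independence. At a placebo rate of 30%, unadjusted detection of a doubling reaches 65%, so low power is not universal either.

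A reader might also infer that removing the correction would make the safety comparison adequate. It would not: detection returns only to the unadjusted figures. The change in how a non-significant result is interpreted matters more than the exemption. This is a cheap improvement to the plan.

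**What to change.** In the Statistics and Data Analysis item:

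1. State after the Simes sentence that the correction does not apply to safety comparisons.
2. Under Hypothesis 2, label the comparisons by side-effect type as descriptive.
3. Report the number of patients affected per arm and the unadjusted risk difference with its 95% confidence interval, overall and by type, with male-only events reported among men.
4. State that a non-significant p-value, corrected or not, is not evidence for Hypothesis 2.

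This costs a few sentences and needs no extra data or patients. The downside is more chance signals, about a 34% chance of at least one false flag over 8 independent null types. The descriptive label deals with that by telling the reader not to treat a single flag as a finding.
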